7.4 Missing Data

All attempts will be made to collect all data per protocol.

- The patients withdrawn from treatment will be followed up regarding their status according to the WHO Ordinal Scale at Day 29 as far as possible (exceptions for patients with withdrawn consent or lost to follow-up) and this data will be the primary source for handling missing data in the study.

Any data point that appears to be erroneous or inexplicable based on clinical judgment will be investigated as a possible outlier.

- If data points are identified as outliers, sensitivity analyses may be performed to examine the impact of including or excluding the outliers. Any substantive differences in these analyses will be reported.

For survival analyses, patients with death as outcome will be censored at Day 29 (Day 60), unless the required event was reached prior to death. Patients who are lost to follow-up or terminate the study prior to Day 29 (Day 60) for other reason than death and prior to observing/experiencing the event will be censored at the time of their last observed assessment. The only time to event analyses is the time to recovery.

For secondary endpoint analyses, the following imputation rules will be used for patients who are lost to follow-up, terminate early from the study, or do not have further outcome data available after discharge for any reason than death:

- Patients with no data collected at the actual time point of interest for other reason than death, the last assessment of their status prior to this time point will be used as a representative for that time point. Especially, if the patient's clinical status scale is 1 or 2 at the last observed assessment, then the patient will be considered to be recovered through Day 29.
- For endpoints assessing total time (oxygen or non-invasive ventilator care), the status for patients with no data collected for other reason than death, will be assumed unchanged from last assessment of the score up to last day in the definition of the endpoint (Day 29). Thus, no extra days will be added for patients without oxygen or patients without non-invasive ventilator care at last assessment.
- Patients that die in the study will be handled as worst case in all the analyses, that is they are considered to be on oxygen need, non-invasive and invasive mechanical ventilator need for all time points following the death.

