- In analyses of oxygen need, patients in ventilator care (non-invasive or invasive mechanical) will be considered in oxygen need for the corresponding time period and patients with death as outcome will be considered in oxygen need for the remainder of the time period of evaluation.
- In analyses of non-invasive ventilator need, patients that require invasive mechanical ventilation will be considered also as having a non-invasive ventilator need. Patients with death as an outcome will be considered as having non-invasive ventilator need from time of death for the remainder of the time period of evaluation.

- In analyses of invasive mechanical ventilator need, patients with death as an outcome will be considered in invasive mechanical ventilator need for the remainder of the time period of evaluation
- The change from baseline in the WHO ordinal scale will use the baseline score and the score at the endpoint using imputation for missing data as stated above, that is the last assessment of their status prior to this time point will be used.
- If the patient is discharged and no further hospitalization data are available, then the patient will be assumed to not have been readmitted. Thus, no additional imputed days on hospitalization will be added to the number of days recorded on available assessments for these patients.

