- Change from baseline in desmosine/isodesmosine will be compared between treatments using ANCOVA models with treatment allocation as a factor and baseline desmosine/isodesmosine as a covariate. Estimated treatment difference with 95% confidence intervals and associated 2-sided p-value will be given.
- Biomarker values that are below the lower limit of quantitation of assay will be reported as the lower limit of quantitation (LLQ)/2.
- Biomarker values may be log transformed if appropriate.

The proportion of patients with recovery at Day 29 will be compared between treatment groups using a logistic regression model adjusting for treatment and COVID disease severity. The difference between treatment arms will be expressed as a difference in proportions as measured by the Cochran Mantel-Haenzel (stratum)-weighted estimator based on the fitted logistic regression model. The delta method will be used to calculate the standard error for the difference and the associated confidence interval [Ge, 2011]. In addition, the raw proportions per treatment group will be given. If 0 events in any of the groups only raw proportions will be given.

Summaries of the results of the secondary analysis for recovery are displayed in Table 10.

Table 10. COSTA analysis tables – Secondary Analysis (Recovery)

Table #	Table Name	Table Contents
	Proportion of Patients with Recovery at 29 Days, ITT	Overall and by Treatment Group 
 • By Age Group • By Sex • By COVID Disease Severity
	Proportion of Patients with Recovery at 29 Days, PP	Overall and by Treatment Group

Patients that die in the study will be handled as worst case in all analyses.

To have an evaluation using all patients we will count an event as the type of need or worse (e.g., patients with oxygen need; non-invasive ventilator need; ventilator need; or with death at time of evaluation will be counted as having data supporting oxygen need), and included in both denominator and numerator.

8.4.1 Time to a recovery state (Day 1 - Day 29; measured in days)

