8.4.2.1 Sub-sets based on post-randomization outcome

Descriptive summaries of the proportion of patients as well as the duration of the worsening following initiation of study medication will be provided for these endpoints:

- Proportion of patients needing re-hospitalization (post-dose Day 1 – Day 60).
 - Applies to the sub-set of patients that were randomized, treated with study medication and discharged from the hospital alive then re-admitted to the hospital for COVID-19 related treatment.
- Proportion of patients and duration of new oxygen use (post-dose Day 1 - Day 29; measured in days).
 - Applies to the sub-set of patients that were randomized and treated with study medication but then had a new need for supplemental oxygen (score worsened to 4, 5 or 6).
 - Or those which improved during hospitalization (to 3) and then their clinical status worsened again (to 4, 5 or 6).
- Proportion of patients and duration of new non-invasive ventilation or high flow oxygen use (post-dose Day 1 - Day 29; measured in days).

- Applies to the sub-set of alive patients that were randomized and treated with study medication but then had a new need for non-invasive ventilation or high-flow oxygen use (score worsened to 5 or 6).
- Or those which improved during hospitalization (to 3 or 4) and then their clinical status worsened again (to 5 or 6)

The total number of days with recorded use will be the sum of all reported days, regardless of whether the days occur consecutively or in disjoint intervals.

8.4.3 Change from baseline in WHO ordinal scale (Days 10 and 29).

Change from baseline in WHO ordinal scale will be compared between treatments using ANCOVA models with treatment allocation as a factor and baseline WHO score as a covariate. Estimated treatment difference with 95% confidence intervals and associated 2-sided p-value will be given.

8.4.4 Total time on supplemental oxygen (Day 1 - Day 29; measured in days).

The total number of days with recorded use will be the sum of all reported days, regardless of whether the days occur consecutively or in disjoint intervals. Results will be summarized by descriptive statistics including medians and quartiles by treatment arm and compared between treatment groups using Wilcoxon rank sum test. Patients that do not reach the specified score on any day will be counted as 0 days.

8.4.5 Total time on non-invasive ventilator use (Day 1 - Day 29; measured in days).

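### Deaths are promised worst-case handling in every analysis, but the SAP's rule does not deliver it for total oxygen days and total non-invasive ventilator days

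*SAP*

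**What the plan says.** SAP 7.4 sets the principle for deaths: "Patients that die in the study will be handled as worst case in all the analyses, that is they are considered to be on oxygen". The same sentence then says what this means in practice: need of oxygen, and "non-invasive and invasive mechanical ventilator need for all time points following the death". SAP 8.4 repeats the principle without the explanation: "Patients that die in the study will be handled as worst case in all analyses".

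The endpoint-specific bullets in 7.4 follow the same pattern. For oxygen, "patients with death as outcome will be considered in oxygen need for the remainder of the time period of evaluation". For non-invasive ventilation, a patient who dies is "considered as having non-invasive ventilator need from time of death for the remainder of the time period of evaluation".

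Two endpoints add up days over a fixed window: 8.4.4, "Total time on supplemental oxygen (Day 1 - Day 29; measured in days"), and 8.4.5, the same for non-invasive ventilation. In both, "The total number of days with recorded use will be the sum of all reported days", and the arms are compared by a Wilcoxon rank sum test. No section gives a patient who dies the maximum score or the lowest rank.

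For time to recovery, 7.4 censors deaths at Day 29 (Day 60) "unless the required event was reached prior to death". Section 8.4.1, which specifies that analysis, censors deaths at Day 29 and states no exception.

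**The concern.** A rule that assigns need after death works for a question such as whether the patient is on oxygen at Day 29. It does not carry over to a sum of days. There, a patient who came off support early and died late picks up only the few days between death and Day 29. Fewer days is the better result, so the Wilcoxon test can rank that death ahead of survivors who simply needed oxygen for longer. This contradicts the property the SAP claims for all its analyses.

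The course is one the SAP itself allows for. Section 8.4.2.1 plans summaries of patients readmitted after live discharge and of patients who improve and then need oxygen or ventilation again. Protocol 5.4 gives a mean hospital stay of 5 days, against a 29-day window.

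Time to recovery raises a separate question. For a patient who recovers and then dies before Day 29, 7.4 and 8.4.1 give different results, and a programmer cannot tell which to follow.

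**Working it through.** The documents state no figure for this point, so there is nothing to reproduce. The rule is applied as written.

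**Inputs.** The window is Day 1 to Day 29, so a survivor can score at most 29 days (8.4.4, 8.4.5). Need is imputed from death to the end of the window (7.4). The SAP does not say whether the day of death counts, so both readings are shown.

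**Formula.** Let *b* be the days on support before death and *D* the day of death.

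- Score, day of death not counted: *b* + (29 − *D*)
- Score, day of death counted: *b* + (30 − *D*)

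On the second reading the score falls short of 29 by (*D* − 1) − *b*, the number of days the patient was alive without support. The rule therefore gives the maximum only if the patient was on support on every day before death.

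| Case | *b* | *D* | Score (not counted / counted) | Ranks better than |
|---|---|---|---|---|
| Oxygen, off after Day 4 | 4 | 25 | 4 + 4 = 8 / 4 + 5 = 9 | a survivor with 10 or more days |
| Oxygen, 5 days, then discharged | 5 | 27 | 5 + 2 = 7 / 5 + 3 = 8 | a survivor with 12 days |
| Never on non-invasive ventilation | 0 | 28 | 0 + 1 = 1 / 0 + 2 = 2 | a survivor with 6 days |
| Early death, on oxygen throughout | 2 | 3 | 2 + 26 = 28 / 2 + 27 = 29 | almost no one: the rule works here |

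With the day of death counted, a death scores fewer days than a survivor with *s* days whenever *D* > 30 + *b* − *s*. For *b* = 2 and *s* = 10 this is *D* > 22, so any death on Days 23 to 29.

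**Effect on the test.** The data here are invented and show only direction and possible size. The 10 v 5 split is taken from protocol 5.2. Tests are two-sided Wilcoxon with normal approximation and continuity correction.

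- Death in the alvelestat arm. Alvelestat survivors 2, 3, 3, 4, 5, 5, 6, 7, 9; placebo 8, 10, 12, 14, 18. With the death scored 9 (SAP rule), it has rank 10.5 of 15 and p = 0.0057. Scored worst, it has rank 15 and p = 0.0232. The SAP rule flatters alvelestat.
- Death in the placebo arm. Alvelestat 2, 3, 3, 4, 5, 5, 6, 7, 9, 10; placebo survivors 8, 10, 12, 14. With the death scored 9, p = 0.012; scored worst, p = 0.007. The SAP rule works against alvelestat.
- Two late deaths in the alvelestat arm, each scoring 7. Alvelestat survivors 3, 4, 5, 6, 7, 8, 9, 10; placebo 5.5, 8.5, 11, 12, 13. p = 0.057 under the SAP rule and 0.358 if both are scored worst.

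In none of the three does the result cross the 5% level.

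**Time to recovery.** Take recovery as a WHO score of 1 or 2. The SAP has no formal definition; this is the working meaning in its carry-forward rule in 7.4. A patient discharged on Day 6 who dies on Day 27 is:

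- an event at Day 6 under 7.4;
- censored at Day 29 under 8.4.1 as written.

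One such patient is 1/10 = 10 percentage points of a ten-patient arm, or 1/5 = 20 points of a five-patient arm.

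**The case against.** The sentence in 7.4 explains its own term: worst case means in need at the time points following death. On that reading the SAP keeps its word, and at any fixed day after death the rule does give the worst category. This stands, and it confines the point to 8.4.4 and 8.4.5. It does not remove the point. The principle is claimed for all analyses, 8.4 repeats it without qualification, and for a sum of days the stated rule is not a worst case. Scoring deaths at the worst rank is one accepted choice among several, but it is the one that matches the SAP's stated intent.

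The consequences are also limited. Neither summed endpoint is in the protocol's list (section 4.0). SAP 7.2 treats all analyses as exploratory, and the study is unpowered. Mortality is tabulated at Days 29, 60 and 90, and each death gets a narrative, so a late death among about 15 patients would be seen. All of this stands and keeps the point minor.

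A reader might infer three stronger things that the documents do not support.

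- **That the plan counts recovered-then-died patients as recoveries.** Only 7.4 does so, and only for time to recovery; 8.4.1 as written censors them. In the Day 29 proportion a patient dead by then is not recovered. Nor is a difference between time to first recovery and status at Day 29 an error in itself: a survivor who relapses produces it too.
- **That two or three patients would be mis-ranked.** The fatality figures in protocol 5.8 (14.9% to 23.5%) would give 15 × 0.149 = 2.2 to 15 × 0.235 = 3.5 deaths. That counts all deaths, from a general inpatient cohort, whereas this trial excludes patients on or about to need invasive ventilation. Only deaths by Day 29 after time off support are affected.
- **That the rule favours alvelestat.** The direction depends on the arm in which the death falls.

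**Conclusion.** The point holds for total oxygen days and total non-invasive ventilator days. The rule in 7.4 does not make deaths the worst case there, and no other section repairs it. A late death after a period off support can rank well inside the survivors: rank 10.5 instead of 15 in the invented 15-patient example. The per-patient scores follow directly from the SAP's rule. The p-values rest on invented data. The number of patients affected cannot be derived from the documents and could be zero.

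For time to recovery the defect is narrower: 7.4 and 8.4.1 conflict on deaths after recovery and must be reconciled. Overall this is a minor error that is cheap to correct.

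**What to change.** 1. In SAP 7.4, for the endpoints in 8.4.4 and 8.4.5, give any patient dead by Day 29 a score of 30 days, one more than a survivor can reach, in place of the days added after death. Print the number of deaths by arm beside each summary. Keep the present rule for status at a fixed day, where it works.
2. For time to recovery, delete the exception in 7.4 for events reached before death. This agrees with 8.4.1 and with the worst-case principle. If time to first recovery is what is wanted, add the exception to 8.4.1 instead and narrow the claim about all analyses in 7.4 and 8.4.
3. While editing, state how deaths are scored in duration of hospitalization (8.4.6), which has no explicit death rule.

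The cost is a few sentences in the SAP before unblinding, with no new data and no change in patient care. The downside is that for patients who die the total becomes a rank score, not a literal count of days. Medians and quartiles should therefore be read with the number of deaths, and means should not be read as days.

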7.5 Interim Analyses

No interim analyses will be performed.

7.6 Safety Analysis

Time to first combined event.

Any patients that are lost to follow-up or terminated early prior to experiencing any of the events will be censored at the day of their last observed assessment.

Patients who complete follow-up but do not experience any of the events will be censored at the day of their Day 29 visit.

8 ANALYSIS

8.1 Descriptive Information

Table 4 lists the summaries for patient disposition, analysis populations and protocol deviations.

Table 4. COSTA analysis tables - Disposition.

Table #	Table Name	Table Contents
	Patient Dispositon.	The disposition of patients by treatment group and include study milestones 
 • Total number screened, randomized, completed 5, 10 days of treatment, completed Day 29, Day 60 and Day 90 follow-ups and withdrawn patients in total and by withdrawal reason.
	Screen Failures.	A summary of the reasons that patients were screened but not enrolled.
	Major Protocol Deviations.	Major protocol deviations summarized by the reason for the deviation, the deviation category, treatment group, COVID disease severity and (separately) site for all patients.
	Analysis Sets	The composition of analysis populations, including reasons for patient exclusion by treatment group.

Table 5 summarizes patient demographics. Demographics include age/DOB, sex, height, weight, BMI (calculated), ethnicity, and race.

Table 5. COSTA analysis tables - Demographics.

Table #	Table Name	Table Contents
	Baseline Demographic Characteristics.	Overall, by treatment group, by COVID disease severity and by baseline clinical

		status assessment using the WHO ordinal scale for ITT, PP and SS (if different).
--	--	----------------------------------------------------------------------------------

Summaries of baseline clinical characteristics are displayed in Table 6. Baseline clinical characteristics include brief physical exam findings, vital signs, clinical status assessment using the WHO ordinal scale score, COVID-19 symptom onset, admission date, COVID disease severity, existing co-morbidities, and COVID-19 standard medications and treatments.

Table 6. COSTA analysis tables - Baseline Clinical Characteristics.

Table #	Table Name	Table Contents
	Baseline clinical characteristics (Eg. WHO ordinal scale score, vital sign values, COVID disease severity, co-morbid conditions - obesity, hypertension, diabetes, asthma, and COPD).	Overall, by treatment group and COVID disease severity for ITT, PP and SS (if different).
	Proportion patients with WHO ordinal scale score of 3, 4 and 5, ITT.	Overall and by treatment group.
	Proportion patients with COVID disease severity of mild, moderate, severe and critical, ITT.	Overall and by treatment group.
	Disease onset (days with COVID symptoms, hospital admission date, COVID disease severity and oxygen need at randomization), ITT.	Overall and by treatment group.
	Number and proportion taking concomitant dexamethasone or remdesivir, ITT.	Overall, by treatment group and COVID disease severity.

8.2 Study Medication Compliance

Summaries of study non-medication compliance are listed in Table 7.

Table 7. COSTA analysis tables - Study Medication Compliance.

Table #	Table Name	Table Contents
	Study Medication Compliance (number of patients who had study medication halted/slowed and the number of patients with missed doses)	The number of patients with discontinued or missed doses (except due to discharge) by treatment group for ITT and PP.
	Patient study medication discontinuation by study day.	By treatment group for ITT and PP.

8.3 Primary Endpoint Analysis

The primary endpoint is safety and tolerability of alvelestat. Safety endpoints include SAEs and AEs. Adverse events will be analyzed using quantitative and qualitative measures.

Treatment-emergent adverse events will be summarized by treatment group for all AEs, related AEs, serious adverse events, deaths, adverse events leading to discontinuation of study medication or to withdrawal from study, adverse events of different severity and adverse events of different chronicity.

Treatment-emergent adverse events will be coded using MedDRA and summarized by system organ class and preferred term for each treatment group.

The time to the composite AE endpoint (death, SAE, severe AE or ET/W of treatment during first 10 days) will be compared between treatment groups using the log-rank test and difference between treatment arms will be expressed as a difference in proportions as measured by the Cochran Mantel-Haenzel (stratum)-weighted estimator based on the fitted logistic regression model

- If '0' events, proportions will be presented.

Summaries of the results of the safety analysis are displayed in **Table 8**.

Table 8. COSTA analysis tables - Safety Analyses.

Table #	Table Name
	Time to first composite AE (Safety Analysis Set)
	Number/Proportion Treatment emergent adverse events summary (Safety Analysis Set)
	Number/Proportion TEAEs leading to discontinuation of study treatment by system organ class and preferred term (Safety Analysis Set)
	Number/Proportion TEAEs with an outcome of death by system organ class and preferred term (Safety Analysis Set)

Deaths, Serious Adverse Events and other Significant Adverse Events

Narratives will be provided for deaths and serious adverse events.

Pregnancies.

For any patients in the Safety population who become pregnant during the study, every attempt will be made to follow these patients to completion of pregnancy to document the outcome, including information regarding any complications with pregnancy and/or delivery.

8.4 Secondary Endpoint Analysis

The biological effect of alvelestat will be assessed through measurement of pharmacodynamic markers of NET activation, elastase activity, inflammation, and coagulopathy as detailed in Table 9.

Table 9. COSTA analysis tables - Biomarker Analyses.

Table #	Table Name	Table Contents
	Descriptive Summary over time and Change from baseline in the amount of NETosis: amount of cell-free DNA, MPO-DNA complexes, and mount of citrullinated histone H3	Overall and by Treatment group Day 1 – Day 5/10/EOT
	Descriptive Summary over time and Change from baseline in blood biomarkers of inflammation (absolute neutrophil count; absolute lymphocyte count; neutrophil-lymphocyte ratio [NLR], C-Reactive protein)	Overall and by Treatment group Day 1 – Day 5/10/EOT
	Descriptive Summary over time and Change from baseline in blood pro-inflammatory cytokines IL-1beta, IL-6, IL-8, TNF-alpha	Overall and by Treatment group Day 1 – Day 5/10/EOT
	Descriptive Summary over time and Change from baseline in d-dimer	Overall and by Treatment group Day 1 – Day 5/10/EOT

Table #	Table Name	Table Contents
	Descriptive Summary over time and Change from baseline in plasma desmosine/isodesmosine	Overall and by Treatment group Day 1 – Day 5/10/EOT

- Change from baseline in markers of NETosis will be compared between treatments using ANCOVA models with treatment allocation as a factor and baseline marker of NETosis as a covariate. Estimated treatment difference with 95% confidence intervals and associated 2-sided p-value will be given.
- Change from baseline in markers of inflammation (e.g. CRP) will be compared between treatments using ANCOVA models with treatment allocation as a factor and baseline inflammatory marker as a covariate. Estimated treatment difference with 95% confidence intervals and associated 2-sided p-value will be given.
- Change from baseline in cytokines will be compared between treatments using ANCOVA models with treatment allocation as a factor and baseline cytokine value as a covariate. Estimated treatment difference with 95% confidence intervals and associated 2-sided p-value will be given.
- Change from baseline in D-dimer will be compared between treatments using ANCOVA models with treatment allocation as a factor and baseline D-dimer as a covariate. Estimated treatment difference with 95% confidence intervals and associated 2-sided p-value will be given.
- Change from baseline in desmosine/isodesmosine will be compared between treatments using ANCOVA models with treatment allocation as a factor and baseline desmosine/isodesmosine as a covariate. Estimated treatment difference with 95% confidence intervals and associated 2-sided p-value will be given.
- Biomarker values that are below the lower limit of quantitation of assay will be reported as the lower limit of quantitation (LLQ)/2.
- Biomarker values may be log transformed if appropriate.

The proportion of patients with recovery at Day 29 will be compared between treatment groups using a logistic regression model adjusting for treatment and COVID disease severity. The difference between treatment arms will be expressed as a difference in proportions as measured by the Cochran Mantel-Haenzel (stratum)-weighted estimator based on the fitted logistic regression model. The delta method will be used to calculate the standard error for the difference and the associated confidence interval [Ge, 2011]. In addition, the raw proportions per treatment group will be given. If 0 events in any of the groups only raw proportions will be given.

Summaries of the results of the secondary analysis for recovery are displayed in Table 10.

Table 10. COSTA analysis tables – Secondary Analysis (Recovery)

Table #	Table Name	Table Contents
	Proportion of Patients with Recovery at 29 Days, ITT	Overall and by Treatment Group 
 • By Age Group • By Sex • By COVID Disease Severity
	Proportion of Patients with Recovery at 29 Days, PP	Overall and by Treatment Group

Patients that die in the study will be handled as worst case in all analyses.

To have an evaluation using all patients we will count an event as the type of need or worse (e.g., patients with oxygen need; non-invasive ventilator need; ventilator need; or with death at time of evaluation will be counted as having data supporting oxygen need), and included in both denominator and numerator.

8.4.1 Time to a recovery state (Day 1 - Day 29; measured in days)

The time to recovery from Day 1 to Day 29 will be compared between treatment groups using a log-rank test; patients not in recovery at end-of study/withdrawal will be censored at last observed time point in the treatment period or at last time status was assessed if collected post treatment-withdrawal. Patients with death as outcome will be censored at the scheduled end-of-study Day 29. Data will be illustrated using Kaplan-Meier plots and the median time to recovery estimated if appropriate.

